## Aim 2. Evaluate differences in infant skin health between 3- and 6-hour bundled care diapering at two sites (buttocks and chest)?

# **RQ1**. Does skin transepidermal water loss (TEWL) differ over time and at the end of 6 weeks between 3- and 6-hour bundled care diapering on the buttocks and chest?

**Analysis:** The trajectories of TEWL measured across the 18 days of bundle care will be fitted using a linear mixed model with a random intercept. We will first determine the best trajectory fit for TEWL over the 18 days. Once we select an appropriate trend for the data a model similar to the one described for weight will be estimated. We will remove technology burden scores and add time varying covariates for time since last bath, urine output, stool pattern, and feeding type indicator.

# **RQ2**. Do neonatal skin condition scores differ over time and at the end of 6 weeks between 3-and 6-hour bundled care diapering?

**Analysis:** We will assess the distribution of the neonatal skin condition score. Based on the distribution we will select the most appropriate link function to fit a generalized linear model with repeated measures. The models to be estimated will be similar to the example model we presented for number of apnea events, including the appropriate link function and distribution. Further, we will remove technology burden scores and add time varying covariates for time since last bath, urine output, stool pattern, and feeding type indicator.

## **RQ3**. Does skin pH differ over time and at the end of 6 weeks between 3- and 6-hour bundled care diapering on the buttocks and chest?

**Analysis:** We will assess the distribution of the pH of chest and buttocks. Based on the distribution, we will select the most appropriate link function to fit a generalized linear model with repeated measures. The models to be estimated will be similar to the example model we presented for number of apnea events, including the appropriate link function and distribution. Further, we will remove technology burden scores and add time varying covariates for time since last bath, urine output, stool pattern, and feeding type indicator. Separate models will be estimated for pH of the chest and pH of the buttocks.

#### **RQ4. Skin Microbiota**

**Analysis:** [name] in Shallowater, TX will provide the microbiome sample analysis services to determine composition of skin microbiome by 16S rRNA pyrosequencing. Funding for the microbiome analyses will come directly from Kimberly Clark's budget. Pyrosequencing data will be analyzed with a workflow based on QIIME software. Data will be compiled and relative percentages of microbes will be determined for each individual sample. Data will also be compiled at each individual taxonomic level according to the NCBI taxonomy criteria. Significance differences in relative abundance of specific taxa between the intervention groups will be calculated using the Kruskal Wallis test.

To assess the extent to which taxonomic diversity at the family and genus level can be used to distinguish microbial communities associated with skin swab samples; Principal Component Analysis (PCoA) will be used. Rarefaction, Chaol, Ace and Shannon indexes will be performed on the data to evaluate if diversity and richness of populations are different among subjects within the different intervention and over time. Demographic and other clinical data will be evaluated for basic correlation with any observed microbiome changes.

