d. Procedures: A neonatal provider will give approval for participation in the study. Parents will be approached for consent after eligibility screening is completed (≤ 32 weeks gestation). The principal investigator is a clinical nurse specialist and nurse scientist who has been affiliated in the Intensive Care Nursery since 1993. Study personnel will explain the study, allow time for questions, have a parent sign the consent form, and a copy will be given to the parent. Parents will provide consent for their infant's participation in the study and will give permission for themselves to participate in an interview about the study, if selected. Five parents from each group will purposively selected to participate in an interview. Parents will be selected to include parents with infants < 1000 grams at birth and parents with infant ≥ 1000 grams at birth.

[figure not shown]
Following consent, the infant will be monitored until all inclusion and exclusion criteria are met. At that time randomized to an intervention group and data collection will be initiated. The intervention will continue for six weeks at which time collection of data will stop and bundled diapered care will resume according to unit protocol. If the infant no longer meets inclusion criteria the intervention will be discontinued and routine data collection will be discontinued. The exclusion criteria will be noted, e.g. use of diaper cream, and data collection regarding any new illness characteristics or treatments will continue. If an infant requires a diaper change due to a stool or other needed procedure this will be recorded on a bedside card.

Ten nurses will be recruited for participation in interviews around intervention acceptability at the end of the study.

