**Table 1. Data Collection** 

Construct	Measure/	Variable	Time frame		
	Instrument				
	Descriptive data to describe the sample				
Maternal history	EMR 	Age, medical hx. of skin disease,	Enrollment		
Infant characteristics	EMR	GA  , birth weight, diagnoses, antibiotics, delivery mode, lab values as required to describe skin health (e.g. albumin, protein, bilirubin) All bundled care event time frames from study entry to study discharge (expected vs. actual bundled times) During bundled care—respiratory support, changes in support, FiO 2 changes, average Daily FiO 2 , caffeine	Enrollment, 3x/week, or as available		
	Aim 1. Infant	Health			
Bundled care	Observation, videotape & EMR	Specific interventions (e.g. suctioning, positioning, offering pacifier, diapering) Length of bundled care events Time between bundled care events	Observer 3x/week for the 3-hour diaper group and 4s/week for the 6-hour group to allow for one within group comparison; Videotaped 1x/week Daily; retrieved 3x/week		
Physiologic stability	GE monitor	1-minute values of heart rate, respiratory rate and oxygen saturation 15 minutes before and after each observed bundled care event	3x/week for the 3-hour diaper group and 4s/week for the 6-hour group to allow for one within group comparison		
	EMR	# bradycardia events daily	Daily; retrieved 3x/week		
	EMR	# apneic events daily	Daily retrieved 3x/week		
	EMR	# desaturation events daily	Daily retrieved 3x/week		
	EMR	Feeding tolerance (emesis, gastric residual volumeml, feeding interruptions)	Daily retrieved 3x/week		
Weight gain	EMR	Daily weight in grams	Daily retrieved 3x/week		
	Aim 1. Covariates				
Development	EMR	Postmenstrual age (PMA)			
Severity of illness	Technology Burden	Total Score 0-100	Retrieved 3x/week to coincide with observation		
	EMR	Time in minutes since the end of the last bundled event	With each observation		

	Aim 2. Skin Health (buttocks and chest)			
Acid mantle	рН	0.00 to 14.00.	3x/week with observation	
development				
Water loss	TEWL	TEWL 	3x/week with observation	
	Dermalab			
Skin status	NSCS⁴	NSCS-range 3-9	Twice daily retrieved	
			3x/week	
Microbiome		Microbiota pattern	3x/week with observation	
	Aim 2. Covariates			
	EMR	PMA		
	EMR	Delivery mode		
	EMR	Time since last bath	3x/week with observation	
	EMR	Daily urine output	3x/week with observation	
	EMR	Time in minutes since the last bundled event		

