	EMR	Stool pattern (categorical)	3x/week with observation	
	EMR	Feeding type (formula vs. breast and route; enteral	3x/week with observation	
		vs. nipple)		
	Bedside	Diaper size and brand	3x/week with observation	
	checklist			
	Stool	Scavenged	1x/week as available	
	Aim 3. Feasibility			
Intervention	Interviews	Parent perceptions	End of infant data	
acceptability			collection;	
and feasibility		Provider perceptions	At study end	
•	Exploratory Health Outcomes			
Late onset	EMR	Presence or absence	Two weeks after end of the	
sepsis			study	
Urinary tract	EMR	Presence or absence	Two weeks after end of the	
infection			study	

<sup>1EMR=electronic medical record; GA=gestational age at birth; TEWL=transepidermal water loss; NSCS=neonatal skin condition score.

- ii. Physiologic measures: Heart rate, respiratory rate, and pulse oximetry will be measured continuously with a GE Cardiopulmonary monitor (standard monitor at DUH) with acquisition from the server, sent to the PI weekly for all enrolled subjects in a data secured zip file. 1-minute values for each 24-hour observation in which a bundled care data collection occurred will be extracted and the required time frames will be extracted for analysis.
- iii. Bundled Care: The content of bundled care will be determined through the observational coding of all caregiving activities during weekly observations (3 times/week for 3-hour diapered and 4 times/week for the 4-hour diapered intervention group; see intervention section above) and 12-hour videotaping (1 time per week for each group) of bundled care events. The length of time for each bundled care event will be operationally defined as beginning when the nurse's hands enter the incubator and will end when the nurse's hands leave the incubator following caregiving.
- iv. Microbiome: One microbiome sample will be taken from the buttocks immediately after the diaper is removed and before the skin is cleaned, if there is NO stool present. A second swab will be collected from the chest at the same time. The following procedure will be used for all microbiome samples. Needed supplies will include a tube of sterile solution of PBS + 0.1%Tween 20 and a Nova Biostorage FLOQ swab with cuvette.
  - a. Remove the swab from the package
  - b. Insert the tip of the swab into the sterile PBS + 0.1% Tween 20 solution until moistened.

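### Aim 2 RQ4: the Kruskal-Wallis test on taxa has no infant-level unit for repeated swabs and no multiplicity control, and as written it does not address either time element of the question

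*Combined protocol and SAP*

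**What the plan says.** Section 2 asks under Aim 2 RQ4 whether the two diapering groups differ in skin microbiota both across the study period and at its six-week end. Table 1 lists the microbiome variable ("Microbiota pattern") three times a week. Section 4.d sets six weeks of intervention, and Section 4.e.iv specifies a buttocks and a chest swab on each occasion. The buttocks swab is taken only "if there is NO stool present". Under Section 4.d, once an infant no longer meets the inclusion criteria, "routine data collection will be discontinued".

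The analysis text for RQ4 in Section 10 states that "relative percentages of microbes will be determined for each individual sample" and that "Data will also be compiled at each individual taxonomic level". The whole between-group analysis of taxa is then one sentence: "Significance differences in relative abundance of specific taxa between the intervention groups will be calculated using the Kruskal Wallis test". Time enters the RQ4 analysis only for the indexes, which are to show whether "diversity and richness of populations are different among subjects within the different intervention and over time", and no test is named for that. The ordination refers to "taxonomic diversity at the family and genus level". The opening of Section 10 sets a two-sided 0.05 threshold for all tests.

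**The concern.** Kruskal-Wallis compares independent observations. Here each infant contributes a series of correlated swabs at each site, and the text does not say what enters the test: one summary per infant, one visit at a time, or every swab. Two analysts could follow the paragraph faithfully and report different results, and neither would need to give a trend or a week-6 difference.

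The taxa test also has no stated correction for the number of taxa, although the Aim 1 RQ2 and RQ4 analyses promise one for their comparisons. The number of taxa, the main taxonomic level and the handling of the two sites are all open. At stake is a false taxon being carried into the larger study that this one is meant to inform, and RQ4 being left without a defined estimate.

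**Working it through.** **1. Data structure.** Inputs: three swabs a week per site (Table 1), six weeks (Section 4.d), two sites (Section 4.e.iv), at least 25 infants per group with complete data (Section 4.b).
- Visits: 3 × 6 = 18, which reproduces the 18 days per infant given in Section 10, Aim 1 RQ1.
- Swabs at full collection: 25 × 18 = 450 per arm per site; 50 × 18 × 2 = 1,800 in all. Real counts will be lower because of stool and early stopping.

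The plan gives no power or error calculation for RQ4, so there is no further figure to reproduce.

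**2. One value per infant, the kindest reading.** With null data, 25 v 25 infants and within-infant correlation (ICC) from 0 to 0.7, the simulated error of Kruskal-Wallis is 4.5–5.7% on the 18-swab mean and 4.3–5.4% on the last swab. The test is valid per taxon once the infant is the unit.

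**3. Several taxa, no correction, one site, one contrast.** For k independent null taxa the chance of at least one false result is 1 − 0.95^k. The correlated column is simulated with correlation 0.5 between taxa. Both k and the correlation are assumptions, because the documents give neither.

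| Taxa tested | Independent, 1 − 0.95^k | Correlation 0.5 |
|---|---|---|
| 3 | 14% | 12% |
| 5 | 23% | 18% |
| 10 | 40% | 29% |
| 20 | 64% | 45% |

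Simulation with independent taxa agrees with the formula (13%, 21%, 40%, 63%). Repeat runs of the correlated case put the 20-taxon figure at 44–45%.

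**4. What the rest of Section 10 does.**
- TEWL: linear mixed model with a random intercept.
- NSCS and pH: generalized linear models with repeated measures; pH is modelled separately by site.
- Taxa: rank test only.

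The TEWL, NSCS and pH models borrow the weight or apnea model, whose declared estimate of interest is the group-by-day term. None declares a week-6 contrast, but a week-6 difference could be computed from each fitted model. The taxa test, as written, yields neither a trend nor a week-6 difference.

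**5. Effect of correction.** Suppose two sites and two contrasts (trend and week 6) are tested, giving four families.
- Benjamini-Hochberg at 5% within each family: simulated chance of any false result about 11–18% overall. As a check, four independent families at 5% give 1 − 0.95^4 = 18.5%.
- Applied jointly over all tests: about 2–5%.
- Power for one taxon truly 1.0 SD apart at one site and contrast, 25 per arm, independent tests: about 92% uncorrected; separate v joint about 78 v 61% with 5 taxa and 58 v 40% with 20.

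**The case against.** **The study is exploratory.** Section 2 states an exploratory purpose, Section 3 repeats it, Section 4.b aims at estimating values and variances, and Section 8 defers conclusions on benefit to larger studies. No decision rests on one taxon. This stands and lowers the weight. It does not remove the point, because the RQ4 text announces significance testing and a study meant to supply estimates needs a defined one. It also cuts the other way: a reader might infer that RQ4 is confirmatory because the exploratory label in Section 2 is attached only to sepsis and urinary tract infection. The overall purpose does not support that.

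**The taxa may be a short list.** The wording allows it. With 3 to 5 taxa the figure is 12–23%: not negligible, but far from certain error.

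**The missing week-6 contrast is not peculiar to RQ4.** Correct. TEWL, NSCS and pH do not declare one either, nor any multiplicity control. A reader might infer that RQ4 alone falls short here. What sets it apart is the lack of any repeated-measures handling from which the contrast could be obtained.

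**Nobody would pool the swabs.** A reader might infer from the per-sample computation that all swabs will be tested as independent. The error per taxon would then be 2 × (1 − Φ(1.96/√(1 + 17 × ICC))), or 23% at ICC 0.1 and 58% at ICC 0.7. The plan does not state such an analysis, nor a separate test at every visit, so these figures are conditional and carry no weight here.

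**The diversity text already refers to subjects.** It does, so that part may be meant at infant level, but it names no test.

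**Conclusion.** The point holds, with minor to moderate weight. As written, the taxa test has no stated unit, no provision for repeated swabs and no control across taxa, and it does not address RQ4's two time elements. With the infant as the unit, the error is about 5% per taxon. The chance of at least one false taxon for one site and one contrast is about 12–14%, 18–23%, 29–40% and 45–64% with 3, 5, 10 and 20 taxa. These figures rest on 25 infants per arm, all taxa null, and an assumed number of taxa with correlation of 0 to 0.5 between them.

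A reader might multiply this over two sites and two contrasts and reach 52–62% with 5 taxa and nearly 100% with 50. The documents do not support that as a description of the plan, because the plan defines neither contrast for taxa and fixes no number of taxa.

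**What to change.** - **Unit and model.** Make the infant the unit, separately by site, and fix one approach in advance. Preferably use a repeated-measures model with an infant random effect, on a scale suited to data with many zeros, giving the group-by-time effect and the week-6 difference from all available swabs. Keep the planned rank test on one value per infant (for example the last-week mean) as a sensitivity analysis. Do not choose between the two by how much data turn out to be missing.
- **Taxa.** Name one main taxonomic level, and either a short list or a prevalence cut-off, in advance. Treat other levels as descriptive.
- **Multiplicity.** Apply Benjamini-Hochberg at 5% across the taxa tested, and state in advance whether it is applied within each site and contrast or jointly. Either choice is defensible: separate families keep more power, and joint use gives lower overall error.
- **Reporting.** Give estimates with 95% CIs for every taxon tested, significant or not. Report by arm how many infants have no last-week swab, and why. Section 4.d gives use of diaper cream as an example of a reason for stopping, and Section 8 ends the intervention on a skin-score criterion. Loss may therefore be related to arm and to the microbiota, and a last-week analysis of those remaining could be biased.

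**Cost.** A paragraph of SAP text and a little more analysis work with routine software; no new data. The real price is power per taxon: from about 92% uncorrected at 1.0 SD to 78% (separate) or 61% (joint) with 5 taxa, and to 58% or 40% with 20. A short list fixed in advance limits that loss.

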## **Research Summary**

NCT03370757

- 1. **Protocol Title** Very Low Birth Weight (VLBW) Preterm Infant Health Outcomes with Bundled Care in the Neonatal Intensive Care Unit: A RCT
- 2. Purpose of the Study Explore the impact of bundling nursing care activities on the overall health of VLBW preterm infants who receive bundled care in a Level IV Neonatal Intensive Care Unit (NICU). Specific study aims include:
  - **Aim 1.** Evaluate differences in infant health when diaper changes occur at 3- versus 6-hours during 3-hour bundled care.
    - **RQ1.** What caregiving activities other than diaper changes are included in *bundled care events* and do they differ when diaper changes are bundled every 3 versus 6 hours.
    - **RQ2.** Does infant physiological stability ( $\Delta$  heart rate,  $\Delta$  respiratory rate,  $\Delta$  oxygen saturation, # apnea # bradycardias, # desaturations, feeding tolerance) differ **between 3- and 6-hour bundled care diapering**?
    - **RQ3.** Does infant weight gain over time differ between 3- and 6-hour bundled care diapering?
    - **RQ4.** Within the 6-hour bundled diaper care group, does infant physiological stability ( $\Delta$  heart rate,  $\Delta$  respiratory rate,  $\Delta$  oxygen saturation) differ between bundled care with and without a diaper change (3 versus 6-hours)?
  - **Aim 2.** Evaluate differences in infant skin health between 3- and 6-hour bundled care diapering at two sites (buttocks and chest).
    - **RQ1.** Does skin transepidermal water loss (TEWL) differ over time and at the end of 6 weeks between 3- and 6-hour bundled care diapering on the chest and buttocks?
    - **RQ2.** Do neonatal skin condition scores differ over time and at the end of 6 weeks between 3- and 6-hour bundled care diapering?
    - **RQ3.** Does skin pH differ over time and at the end of 6 weeks between 3- and 6-hour bundled care diapering?
    - **RQ4.** Does the skin microbiota differ over time and at the end of 6 weeks between 3- and 6-hour bundled care diapering?
  - **Aim 3.** Evaluate the acceptability and feasibility of conducting a bundled care intervention where the frequency of one care activity, diaper care, is standardized.
    - **RQ1.** What are the perceptions of parents and providers about the criteria necessary for conducting a diaper change in the NICU?
    - **RQ2.** What are the perceived barriers of parents and providers to longer timeframes between diaper changes?

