### 4. Design & Procedures

**a. Design and Setting.** A randomized controlled designed will be used to evaluate the effect of *bundled diaper care* on overall infant and skin health. Infants will be recruited from the Level IV Intensive Care Nursery (ICN) at Duke University Hospital. The ICN is a Level IV, 67-bed nursery and one of the area's leading referral centers for infants born prematurely. The

Duke ICN has an average daily census of 90% and annually admits 150 VLBW infants. The ICN practices individualized developmental care with standard bundled care intervals that vary based upon an infant's birth weight and feeding status (every 3, 4, or 6 hours). Infants who are admitted or transferred to one of the ICN three stepdown units will also be considered if eligible and will continue to receive the intervention when transferred including the Special Care Nursery at Durham Regional Hospital. The principal investigator has been a clinical nurse specialist affiliated with the ICN since 1993 and has the support of the nursery medical and nursing team to conduct this research including the Division of Neonatology, the ICN Intensive Care Developmental Care Team and the Medical Director.

**b. Participants.** A maximum of 80 VLBW infants will be recruited to ensure at least 25 infants in each study group with complete data. Ten parents of infant participants (5 in each study group) and 10 health care providers will participate in interviews about the acceptability and feasibility of the diapered bundled care intervention. The goal of this study is to enrich the literature with estimation of values and variances of the outcomes measured as well as how these values change over time. With a total sample size of 50 VLWB infants, we are confident that we will be able establish effect to inform a larger subsequent study. Because most of the infants are expected to receive care up to 6-weeks, we expect little missing data or participant attrition.

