### 10. Data Analysis and Statistical Considerations

Initially, we will conduct descriptive analyses, including examination of means and proportions and the measures of variability for each variable overall and by bundled care groups. The descriptive analyses will be followed by modeling approaches to respond to the research questions. Tests of statistical significance will be two-sided and the threshold for statistical significance will be P < 0.05.

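### RQ4 on the skin microbiota gets no overall between-arm answer: the plan tests arms only taxon by taxon, and names no test or model for the ordination or the diversity indices

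*Combined protocol and SAP*

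**What the plan says.** The research question (section 2, Aim 2 RQ4) is "Does the skin microbiota differ over time and at the end of 6 weeks between 3- and 6-hour bundled care diapering".

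The analysis is in section 10, Aim 2 RQ4 Skin Microbiota, and has three parts:

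- **Single taxa.** "Significance differences in relative abundance of specific taxa between the intervention groups will be calculated using the Kruskal Wallis test". No adjustment for the number of taxa is stated.
- **Ordination.** The aim is to see how far taxonomic diversity at family and genus level "can be used to distinguish microbial communities associated with skin swab samples; Principal Component Analysis (PCoA) will be used". Arm is not mentioned, and no distance measure or test follows.
- **Diversity and richness.** "Rarefaction, Chaol, Ace and Shannon indexes will be performed on the data", with the purpose "to evaluate if diversity and richness of populations are different among subjects within the different intervention and over time". No test or model is named.

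The opening of section 10 adds a general rule: "Tests of statistical significance will be two-sided and the threshold for statistical significance will be P < 0.05". That is a threshold, not a method. On sample size, section 4.b states: "A maximum of 80 VLBW infants will be recruited to ensure at least 25 infants in each study group with complete data".

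**The concern.** RQ4 is a question about arms. An ordination returns coordinates for the samples. It does not return an estimate or a p-value for arm, so any separation would be judged by eye. The indices could each give a single between-arm answer, but how they would be compared is left open.

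Two things are at stake. First, a change spread thinly over many taxa can be missed when each taxon is tested alone. Second, if the distance, index, time point and test are chosen once the data are in hand, the reported answer depends on choices nobody fixed in advance. That matters for a study meant to inform a larger one.

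**Working it through.** **1. Side-by-side reading of Aim 2 in section 10**

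| Question | Between-arm method named | Repeated measures handled |
|---|---|---|
| RQ1 TEWL | Linear mixed model, like the weight model (arm, day, arm-by-day) | Yes, random intercept |
| RQ2 skin score | Generalized linear model, like the apnea model | Yes |
| RQ3 pH | As RQ2, separate models for chest and buttocks | Yes |
| RQ4 single taxa | Kruskal-Wallis | Not stated |
| RQ4 ordination | None | Not stated |
| RQ4 diversity indices | None; intent stated | Not stated |

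RQ4 does not refer back to the models of RQ1–RQ3. Aim 1 RQ2 and RQ4 promise control for multiple comparisons; Aim 2 RQ4 does not. The plan gives no microbiome effect size, SD or power, so there is no figure to reproduce beyond 2 × 25 = 50 infants.

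**2. Can the taxon tests stand in for an overall test?**

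For K independent taxa each tested at 0.05, the chance of at least one false positive is 1 − 0.95^K:

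- K = 10: 40%
- K = 20: 64%
- K = 30: 1 − 0.215 = 79%
- K = 50: 92%

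Simulated null trials with 30 genera gave about 75%. K is an assumption. So one significant taxon, without adjustment, does not answer RQ4.

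**3. What would an overall test add?**

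Simulation, all inputs assumed: 25 infants per arm, one profile per infant, 30 genera, log-normal abundance with SD 1.2, no zeros. Taxon tests are rank tests with Benjamini-Hochberg control, counted as a success if any genus is flagged. The overall test is a permutational MANOVA. The runs included sets of 400 trials with 499 permutations and 300 trials with 299. Ranges span the runs, several of which varied the spread of baseline genus abundance.

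| Scenario | Taxon tests | Overall, Aitchison | Overall, Bray-Curtis |
|---|---|---|---|
| No difference | 3–4% | 3–5% | 4% |
| All genera shift 0.3 SD, half up, half down | 32–45% | 91–95% | 36–84% |
| 30% of genera shift 0.4 SD | 24–28% | 60–63% | 17–41% |
| Two genera shift 1 SD | 75–78% | 79–84% | not run |
| One genus shifts 1 SD | 42–54% | 38–44% | not run |

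With 300 trials the standard error near 45% is √(0.45 × 0.55 / 300) = 2.9 percentage points, so the last two rows show little or no difference.

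**4. What can a diversity index show at this size?**

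With one value per infant, 25 per arm and two-sided 0.05, the difference detectable with 80% power is (1.960 + 0.842) × √(2/25) = 0.79 SD. Power is 42% at 0.5 SD and 81% at 0.8 SD.

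**5. Why the infant must be the unit**

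Swabs three times a week for 6 weeks give up to 3 × 6 = 18 per infant and site. If all 18 were pooled as independent in a Kruskal-Wallis test, the simulated type I error was 0.06, 0.23, 0.42 and 0.52 at assumed within-infant correlations of 0, 0.1, 0.3 and 0.5 (2,000 runs each). The plan does not say that they would be pooled; it does not say what the unit is.

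**The case against.** The best case for the plan is this. A between-arm test does exist, at taxon level, and RQ4 does not ask for one global statistic. The study is sized for estimating values and variances, designates no primary outcome and claims no power, so describing indices and an ordination by arm partly serves its aim. The large power gain comes from assuming a diffuse shift, for which the documents give no basis. The taxon comparator above includes false-discovery control that the plan does not state. The simulations contain no zeros, although sequencing data do. Much of the gain also depends on the log-ratio distance rather than on having an overall test.

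Those points stand, and they limit the size of the claim and its seriousness. They do not supply the missing method: RQ4 is a listed question, and its community-level part has none.

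Two stronger readings are tempting and should not be adopted:

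- A reader might infer from the phrase about subjects within the intervention that the indices are not to be compared between arms at all. The wording is clumsy, but it names both intervention and time. The comparison is intended; only its test is missing.
- A reader might infer that the mismatch between the ordination's name and its abbreviation is what leaves RQ4 unanswered. Principal component analysis works on the abundances, and principal coordinates analysis (PCoA) on a chosen distance matrix, but neither tests arm. The abbreviation, beside a QIIME-based workflow, suggests which was meant. This is a wording correction.

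**Conclusion.** The point holds in this form: the only specified between-arm test of the microbiota is taxon by taxon, without stated multiplicity control, and the community-level analyses have no distance measure, test or model. RQ4 therefore gets no overall between-arm answer, either over time or at 6 weeks.

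That conclusion rests on the text alone. The size of the benefit from closing the gap is illustrative: large if a shift is spread over many taxa, absent or slightly reversed if one taxon carries it, and strongly dependent on the distance. A reader might infer that an overall test is always more powerful; the figures do not support that. The case for it is a single pre-specified answer with controlled error.

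The change should be made, but in an exploratory study sized for estimation the gap does not undermine the trial.

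**What to change.** In section 10, Aim 2 RQ4:

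1. **Overall composition.** For each site (buttocks, chest), pre-name one permutational MANOVA of arm on a pre-named distance, for example Aitchison, with Bray-Curtis as sensitivity analysis. Either use one profile per infant (the week-6 swab or an infant-level average) or keep all swabs and permute whole infants. Permute within the birth-weight strata used for randomization. State the rule for a missing week-6 swab, since section 4.e allows a buttocks swab only when no stool is present.
2. **Diversity.** Analyse Shannon and Chao1 per swab, by site, in the mixed model planned for TEWL: arm, time, arm-by-time, infant random intercept. Report the arm-by-time term and the arm difference at week 6 with confidence intervals, so that both halves of RQ4 are answered.
3. **Hierarchy.** Take the overall RQ4 answer from items 1 and 2. This is two permutation tests and 2 indices × 2 sites = 4 models, so say whether they are adjusted jointly or reported as exploratory. Treat taxon-level tests as follow-up, with false-discovery control and one value per infant.
4. **Wording.** Name the ordination principal coordinates analysis and run it on the same distance.

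Cost: SAP text and a little more analysis on swabs already planned, with no extra sampling. The log-ratio distance needs a small constant added to zero counts. The simulations did not test its effect, which is one reason to keep Bray-Curtis as a check.
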